Potential research subjects have the ability to review the informed consent and DHEA flyer through MyChart prior to any clinic visit. The flyer provides a description of the program and its processes in layman's terms. These items are intended to augment the consenting process and provide a useful tool for the consenter and consentee to communicate. The potential subject will also have the option within MyChart to indicate whether they are interested in consenting to the study prior to their visit. The Arkansas Clinical Data Repository (AR-CDR) will be utilized to find and recruit subjects who may meet eligibility criteria. Information requested from AR-CDR will be a list of female patients between the ages of 18 and 70 years old with a history of breast cancer who are currently on an aromatase inhibitor and have been for at least 6 months. Patients who fit these criteria will be contacted via email, phone, or patient portal and asked if they are interested in learning more about the study. If they are, a study staff member may contact the patient via email, phone or patient portal to discuss further. If a patient prefers to not be contacted, they can opt out of further communications by responding via email, phone or patient portal to notify the research team.

Females of childbearing age and potential must have negative pregnancy test at screening. Subjects who are post-menopausal (as defined in the inclusion criteria) will not require a

IRB 239531 Sponsor: UAMS Version 15 0/7/07/2023 Page 8 of 22

pregnancy test.

At baseline, subjects will undergo a physical exam including clinical breast and gynecological exam. During gynecologic exams, the vaginal pH will be determined and a swab of vaginal epithelium will be sent to pathology to calculate the VMI. These will be used as objective physiologic markers to determine the improvement in vaginal atrophy. The cytologists reading the specimens will be blinded. If the VMI results are "unsatisfactory", the swab of vaginal epithelium will need to be recollected within 4 weeks of Day 1, Week 1 to calculate a new VMI.

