The efficacy population will include all subjects with a baseline assessment who have received at least two weeks of treatment with either Intrarosa® or Replens™. Subjects who discontinue participation in the study (stop the assigned treatment, withdraw consent, etc.) before 2 weeks of treatment will not be included in the efficacy population. Subjects who discontinue participation in the study after 2 weeks but prior to 12 weeks will be included in the efficacy analysis. These subjects will be invited to complete the end of study evaluation at the time of discontinuation; these evaluation values will be included in the efficacy analyses.

The safety population will include all subjects who received at least one administration of either Intrarosa® or Replens™.

Efficacy Endpoints

The primary efficacy endpoint is VMI Response, which is defined as the change in the subject's calculated VMI from baseline to the end of treatment at 12 (±1 week).

Secondary efficacy endpoints: Secondary efficacy endpoints for all study subjects will be determined both at baseline and at the end of treatment. They consist of the following:

- Vaginal pH
- Dyspareunia and vaginal dryness scores on the BSSC-W and the FSFI,
- Quality of life using the QOL-CSV.

IRB 239531 Sponsor: UAMS Version 15 0/7/07/2023 Page 18 of 22

Analysis Plan

Descriptive Analysis: Each efficacy endpoint will be summarized by treatment group and time point as the mean, standard deviation (SD), minimum, 1st quartile, median, 3rd quartile, and maximum. Within each subject, the endpoint's response to treatment will be defined (and calculated) as the endpoint's value at 12 weeks minus its value at baseline; the resulting endpoint responses will be summarized by treatment group as the mean, SD, minimum, 1st quartile, median, 3rd quartile, and maximum. Graphical displays will consist of box plots and scatter plots along with profile plots, a.k.a. "spaghetti plots", that show how the individual subjects respond over time to their assigned treatment. Adherence to distributional assumptions will be assessed, and data transformation to increase such adherence will be implemented, if warranted.

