Primary Efficacy Analyses: To determine each treatment arm's VMI response to treatment, the Intrarosa® arm will be compared to the ReplensTM arm for the difference in their VMI responses using Student's t-test if group variances are equal, Welch's t-test if group variances are unequal, or Wilcoxon's rank-sum test if data violate normality assumptions. In keeping with the research hypothesis that the Intrarosa® arm will exhibit greater improvement in the VMI when compared to the ReplensTM arm after 12 weeks (± 1 week) of treatment, this primary-efficacy comparison will be conducted using a one-sided test at an $\alpha = 0.05$ significance level to look specifically for increased VMI response in the Intrarosa® arm. The follow-up of this primary-efficacy comparison will be analyzed using an ANCOVA model that has 12-week VMI as the outcome variable, treatment arm as the factor of interest, and baseline VMI as the continuous covariate.

Secondary Efficacy Analyses: For each secondary endpoint, the treatment arms will be compared for a difference in the endpoint at baseline, a difference in the endpoint at 12 weeks (± 1 week), and a difference in the endpoint's response to treatment. All comparisons will be conducted using 1-sided tests that employ a multiple-comparison-adjusted $\alpha = 0.01$ significance level to look specifically for improvements with Intrarosa® compared to Replens™. The tests will consist of Student's t-test, Welch's t-test, or Wilcoxon's rank-sum test depending on the endpoint's adherence to distributional assumptions. In follow-up analysis, each secondary endpoint will be analyzed using an ANCOVA model that has the endpoint's 12-week value as the outcome, treatment arm as the factor of interest, and endpoint's baseline value as the continuous covariate.

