Sample Size and Power: The study is powered to detect an effect size of 0.8 SDs for the expected improvement in VMI response among subjects on the Intrarosa® arm compared to subjects on the ReplensTM arm. Specifically, if the study meets its enrollment goal of 60 subjects (30 in each treatment arm), then 30 subjects per arm provide Student's t-test and Wilcoxon's rank-sum test (both 1-sided at $\alpha = 0.05$) with 92.2% power and 91.2% power, respectively, to detect an effect size of 0.8 SDs in VMI response. Moreover, even if the study were to suffer an attrition rate of 20%, then the remaining 24 subjects per arm (48 subjects that remain) still provide Student's t-test and Wilcoxon's rank-sum test (both 1-sided at $\alpha = 0.05$) with 86.1% power and 84.9% power, respectively, to detect an effect size of 0.8 SDs in VMI response.

To see that a 0.8-SD effect size is reasonable for VMI response, we call attention to the studies of Archer *et al.* [14] and Labrie *et al.* [8]. Although neither study utilized VMI itself as the outcome, both studies utilized the percentages of P and S cells as outcomes when reporting the 12-week differences they observed between their DHEA (6.5mg) arms and their placebo arms. Archer *et al.* [14] observed treatment-arm differences of 1.52 SDs in %P cells and 1.02 SDs in %S cells at 12 weeks, whereas Labrie *et al.* [8] observed treatment-arm differences of 1.11 SDs in %P cells and 0.99 SDs in %S cells at 12 weeks. These prior observations of \geq 1-SD effect sizes for VMI-related endpoints show that it is reasonable to expect an effect size of 0.8 SDs for VMI response,

IRB 239531 Sponsor: UAMS Version 15 0/7/07/2023 Page 19 of 22

and thus that our study has sufficient power to achieve its research objectives.

Ethical Considerations

This study will be conducted in accordance with all applicable government regulations and University of Arkansas for Medical Sciences research policies and procedures. This protocol and any amendments will be submitted and approved by the UAMS Institutional Review Board (IRB) to conduct the study.

A Partial HIPAA Waiver for Recruitment will permit study staff to prescreen potential subjects prior to obtaining consent/HIPAA authorization to determine use of prohibited medical products requiring either an 8-week or 6-month washout in order to meet eligibility.

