Note: Thirty subjects/arm (60 subjects) give the 1-sided Student's t-test 92.2% power at α = 0.05 to detect a 0.8-SD increase in VMI Response with Intrarosa® compared to Replens™. Under 20% attrition, the remaining 24 subject/arm (48 subjects) still provide the 1-sided Student's t-test with 86.1% power at α = 0.05 to detect the 0.8-SD increase in VMI Response.

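### Improvement, not an error: name the planned baseline-adjusted ANCOVA as the single primary VMI analysis, in place of an unadjusted test chosen from the data

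*Combined protocol and SAP*

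**What the plan says.** All references are to the combined protocol and SAP.

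- **Efficacy Endpoints:** the primary endpoint is "VMI Response, which is defined as the change in the subject's calculated VMI from baseline to the end of treatment", at 12 weeks.
- **Primary Efficacy Analyses:** the arms are compared on that change, one-sided at 0.05, "using Student's t-test if group variances are equal, Welch's t-test if group variances are unequal, or Wilcoxon's rank-sum test if data violate normality assumptions". No diagnostic, threshold or order is given for the variance and normality checks.
- **Same section:** "The follow-up of this primary-efficacy comparison will be analyzed using an ANCOVA model that has 12-week VMI as the outcome variable", with arm as factor and baseline VMI as covariate. Its alpha and sidedness are not stated.
- **Descriptive Analysis:** "Adherence to distributional assumptions will be assessed, and data transformation to increase such adherence will be implemented, if warranted". The text does not say whether this reaches the primary test.
- **Efficacy and Safety Populations:** "The efficacy population will include all subjects with a baseline assessment who have received at least two weeks of treatment". Under Study Design and Procedures, at the baseline exam "a swab of vaginal epithelium will be sent to pathology to calculate the VMI".
- **Sample Size and Power:** for Student's and Wilcoxon's tests with 24 per arm, "with 86.1% power and 84.9% power, respectively, to detect an effect size of 0.8 SDs in VMI response". The note in Appendix B repeats the t-test figures: "Thirty subjects/arm (60 subjects) give the 1-sided Student's t-test 92.2% power".

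**The concern.** Two features of the primary analysis leave something unused.

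First, the test is settled only after the data are seen. Student's and Welch's tests share one mean difference, so choosing between them does not change what is estimated. The Wilcoxon branch does change the measure behind the primary p-value, as would a transformation if it were applied.

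Second, an unadjusted change score fixes the slope of 12-week VMI on baseline at 1. When the true slope differs from 1, ANCOVA has a smaller residual variance. It also corrects chance baseline differences, which matter more in a trial of 60.

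At stake are precision and having one primary effect estimate fixed in advance. The validity of the test is not in question.

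**Working it through.** **1. The plan's figures.** Inputs from Sample Size and Power: 0.8 SD of VMI change, one-sided 0.05, n = 30 or 24 per arm. Noncentral t with df = 2n − 2 and noncentrality 0.8 × √(n/2):

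- n = 30: 0.8 × √15 = 3.098, df 58, power 92.2%.
- n = 24: 0.8 × √12 = 2.771, df 46, power 86.1%.

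Both match. Replacing n by n × 3/π gives 91.1% and 84.6% for Wilcoxon's test, close to the stated 91.2% and 84.9%.

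**2. ANCOVA for the same true effect.** The correlation ρ and the SDs are not in the documents, so they are assumed. Let k = baseline SD / 12-week SD. Then

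residual variance / change-score variance = (1 − ρ²) / (1 + k² − 2ρk).

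The effect becomes 0.8 / √ratio, with df = 2n − 3. Example, k = 1 and ρ = 0.5: 0.75/1 = 0.75; 0.8/√0.75 = 0.924; noncentrality 0.924 × √12 = 3.200; df 45; power 93.4%.

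Averaging over chance baseline imbalance multiplies the variance by 1 + F/(2n − 2), with F on 1 and 2n − 2 df. At 24 per arm (t-test 86.1%):

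| k | ρ | variance ratio | power | power, averaged over imbalance |
|---|---|---|---|---|
| 1 | 0.3 | 0.650 | 95.9% | 95.6% |
| 1 | 0.5 | 0.750 | 93.4% | 92.9% |
| 1 | 0.6 | 0.800 | 92.0% | 91.5% |
| 0.75 | 0.3 | 0.818 | 91.5% | 91.0% |
| 0.75 | 0.5 | 0.923 | 88.4% | 87.8% |
| 0.75 | 0.6 | 0.966 | 87.1% | 86.5% |
| 0.5 | 0.3 | 0.958 | 87.4% | 86.7% |
| 0.5 | 0.5 | 1.000 | 86.1% | 85.4% |
| 0.5 | 0.6 | 0.985 | 86.6% | 85.9% |

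The slope is ρ/k. At k = 0.5 and ρ = 0.5 it equals 1, the least favourable case under a linear model: 86.1 − 85.4 = 0.7 point lost. At 30 per arm the loss is 92.2 − 91.8 = 0.4 point.

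**3. Chance imbalance.** With equal SDs, a baseline difference of 0.25 SD shifts the change contrast by (1 − ρ) × 0.25 / √(2(1 − ρ)) change-SDs. That is 0.15 at ρ = 0.3 and 0.10 at ρ = 0.7, against a planned effect of 0.8.

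**4. Does choosing the test inflate type I error?** The plan names no criterion, so the simulations assumed Shapiro-Wilk checks followed by Levene's test. With 20,000 trials per scenario at 24 per arm, the rule's error was 4.9-5.5% over normal and floor-bound data. A separate run of 8,000 trials at 30 per arm, with normal and exponential errors, gave 4.8-5.8%, where fixed tests gave 4.5-6.0%. No material inflation appears.

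**5. Floor and skew.** VMI is %S + 0.5 × %I. Table 1 gives 25% I and under 5% S after menopause, so VMI is 12.5 to 17.5, roughly 15 on a 0-100 scale. An assumed floor-bound scenario used beta-distributed VMI with baseline mean 15 and SD 11.9, 12-week means 20 and 35.6 with SDs 20.0 and 23.7, ρ = 0.47 and an effect of 0.80 SD:

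| per arm | Student | Wilcoxon | selection rule | ANCOVA |
|---|---|---|---|---|
| 24 | 85.7% | 86.8% | 86.7-87.1% | 84.9% |
| 30 | 92.6% | 93.4% | 93.5-93.6% | 92.3% |

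At 24 per arm ANCOVA is 86.8 − 84.9 = 1.9 points below the rank test and 1.8-2.2 below the rule. HC3 robust errors lower ANCOVA further, to 83.6%. With exponential 12-week errors, equal SDs, ρ = 0.7 and 30 per arm, ANCOVA had 94.1% against 97.5% for Wilcoxon's test, a gap of 3.4 points, and 91.8% for Student's test.

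**The case against.** The strongest reply is that nothing is broken. The primary test is valid and correctly powered, mean VMI response by arm is reported whichever test is used, and the ANCOVA will be run anyway. The power gain is not established for this trial: the most favourable figures need equal SDs, whereas a population near the VMI floor may well have a smaller baseline spread. In the floor-bound scenario ANCOVA loses. Amending version 15 of an open-label protocol also needs IRB approval, and the documents do not show whether outcome data already exist.

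Most of this stands, and it limits the claim. It does not remove the case for the change. A follow-up ANCOVA with no stated alpha or sidedness does not determine the primary result; a primary one does. The amendment burden is real but small, and the question of existing data is met by requiring the change before outcomes are examined.

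A reader might infer more than the documents support:

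- That choosing the test from the data inflates type I error. The simulations show near-nominal rates.
- That the stated powers are wrong. They reproduce.
- That the t-test power is a lower bound for ANCOVA. ANCOVA falls to 85.4% under a linear model and 84.9% in the floor-bound scenario, both below 86.1%.
- That a transformation will be applied to the primary test. That sentence sits under Descriptive Analysis, and its reach is unstated.

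**Conclusion.** The point holds as a low-cost improvement. The sure benefits are one effect estimate fixed in advance and correction for chance baseline imbalance. Better precision is usual but not guaranteed.

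At 24 per arm, the nine linear-model settings run from 0.7 point below the t-test's 86.1% (86.1 − 85.4) to 9.5 points above it (95.6 − 86.1). Under skew, a loss of about 2 points against the rank test or the plan's own rule is plausible, and 3-4 points is possible with strongly skewed errors. All of these rest on assumed correlations, SD ratios and distributions. The change is worth making, but it should be justified by pre-specification and baseline adjustment, without promising a power gain.

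**What to change.** In Primary Efficacy Analyses, before outcome data are examined:

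- Name the existing ANCOVA (12-week VMI on arm and baseline VMI) as the single primary analysis at one-sided 0.05, reporting the adjusted mean difference and its confidence interval.
- State that no data-driven choice of test or transformation applies to it.
- Keep Welch's t-test and the rank-sum test on VMI change as prespecified sensitivity analyses. The rank-sum test covers the skewed case.

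The endpoint definition can stay: with baseline as covariate, the arm coefficient is identical for 12-week VMI and for change. In Sample Size and Power and the Appendix B note, keep the stated powers but label them as those of the unadjusted t-test and, where given, Wilcoxon's test. Do not call them a lower bound for ANCOVA.

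**Cost:** wording, an IRB-approved amendment and one degree of freedom, plus the possible power loss under skew. No new data are needed and the sample size is unchanged. No subject is lost, because the change score already requires both VMI values.

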Appendix A: Study Calendar

	Pre- Study/Baseline ^a	Day1, Week 1 ^b	Week 2-12	End of Treatment ^c
Determine eligibility for study:	Χ			
Study consent discussed and signed	Χ			
Pregnancy test ^d	Χ			
Collect relevant disease-related data (mammogram, Pap				
smear)e, FSH levelf, baseline conditions, height, weight, and	X			
medical history				
Complete BSSC-W	Χg			Χg
Complete FSFI ^h	Χg			Χg
Complete DHEA Trial Clinical Supplemental Survey	Χg			
Physical exam (including gynecologic ⁱ and breast exams)	Χ			\mathbf{x}^{j}
Vaginal pH to be determined	Χ			X
Swab of vaginal epithelium collected and sent to pathology to calculate VMI ^k	X			х
Estradiol level ^l	Х			Х
Complete QOL-CSV	Χg			χg
Randomize to treatment arm	Χ			
Assigned treatment and study diaries dispensed to subject		Х		
Self-administration (starts same day as dispensed)				
Intrarosa® 6.5 mg insert nightly				
~OR~		x	x	
 Replens[™] 6.7 g prefilled applicator intravaginal two non- consecutive nights weekly 				
Collect AEs ^m		Х	Х	Х
Diary Submissions			Xn	Χo
Drug boxes and unused products collected from subject				Х
Follow up call			x ^p , ^q	

a Pre-study/Baseline should be completed within 28 days prior to Day 1, Week 1.

b Day 1, Week 1 visit may be done the same day as Pre-Study/Baseline visit if all Pre-Study/Baseline activities are completed and eligibility has been confirmed prior to Day 1, Week 1 activities.

c End of Treatment should be completed at week 12 from Day 1, Week 1, i.e., Week 12 ±1 week).

d Subjects who are post-menopausal will not require a pregnancy test. SoC pregnancy test results may be used if completed within 7 days of Day 1, Week 1.

e Mammogram (if deemed appropriate by the treating physician) and normal Pap must be documented within 12 months prior to study entry. If these are not documented in the medical history, they will be obtained for the study. SoC Pap and mammogram (if appropriate) may be used if completed within 28 days of Day 1, Week 1. Pap is not required for females whose cervix has been removed by surgery for reasons not related to cervical cancer or serious cervical pre-cancer.

f If FSH level is not documented in the medical history, one will be obtained prior to study entry.

g Should be completed in-person but can be completed over the phone, if necessary.

h FSFI is to be completed only if participant answers no to question 1 on the coinciding BSSC-W.

i Gynecologic exam, including vaginal pH and VMI activities can take place on the same day as consent and Day 1, Week 1 as long they are completed after consent, all other eligibility criteria have been met, and prior to Day 1, Week 1 activities. SoC breast and pelvic exams may be used if completed within 28 days of Day 1, Week 1.

j During the gynecologic exam, a Pap smear may be performed at the treating physician's discretion if abnormal cervical changes are suspected.

k If the VMI results are "unsatisfactory", the swab of vaginal epithelium will need to be recollected within 4 weeks of Day 1, Week 1 to calculate a new VMI.

A report will be sent to FDA for any subject with an estradiol level out of the normal postmenopausal range at week 12 (±1 week).

m All AEs reported during clinic visits, on diaries, by phone or email, etc. are to be documented, assessed by the PI or designee, and tabulated.

n Diary progress should be submitted after Week 4 (±1 week), Week 8 (±1 week) of treatment. Diaries can be submitted in person, via self-addressed envelope to CTO, text photos to the research nurse cellphone, email photos to the research nurse email, sent photos through MyChart, or faxed to CTO. There will be no deviation for subjects who do not submit diary progress at Week 4 or Week 8.

o Diary progress should be submitted after Week 12 (±1 week) of treatment, or end of treatment. Diaries can be submitted in person, via self-addressed envelope to CTO, text photos to the research nurse cellphone, email photos to the research nurse email, sent photos through MyChart, or faxed to CTO. There will be a deviation for subjects who do not submit diary progress at Week 12 or if they come off treatment early.

Follow-up call should occur at 1 week ±3 days after Day 1, Week 1.

q Follow-up call should occur at 6 weeks ±1 week after Day 1, Week 1.

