All AEs will be analyzed, tabulated and organized by organ-system based on NCI CTCAE v5 and included in the primary analysis.

Diary progress should be submitted after Week 4 (±1 week), Week 8 (±1 week), and Week 12 (±1 week) of treatment. Diaries can be submitted in person, via self-addressed envelope to the cancer clinical trials office, text photos to the research nurse cellphone, email photos to the research nurse email, sent photos through MyChart, or faxed to the cancer clinical trials office. There will be no deviation for subjects who do not submit diary progress at Week 4 or Week 8. There will be a deviation for subjects who do not submit diary progress at Week 12 (or by the end of study

IRB 239531 Sponsor: UAMS Version 15 0/7/07/2023 Page 9 of 22

participation, if they end treatment early).

Compensation is available to subjects upon submission of diaries and completion of study-related activities. The first payment of \$25 will be made to the subject upon submission of diary at Week 4 and completion of the Week 6 phone call. The second payment of \$50 will be made to the subject upon completion of the Week 12 visit, which includes clinic attendance for physical exam, estradiol level, and return of questionnaires/survey, diaries, drug boxes, unused products/packaging. Subjects will be issued a Greenphire Clincard, which will be used to receive payment and funds will be available for use within 1 business day once approved to be released to the card.

See Appendix A: Study Calendar for summary of study protocol and procedures.

Randomization

Subjects who complete the screening will be randomly assigned to either the Intrarosa® or Replens™ arm in a 1:1 ratio. Subjects randomized to the Intrarosa® arm will use 6.5 mg daily for 12 weeks (±1 week). Subjects randomized to the Replens™ arm will use a vaginal applicator two times per week for 12 weeks (±1 week).

The study coordinator will use the Research Participant Registry System (RPRS) to randomize subjects to either the Intrarosa[®] arm or the Replens[™] arm. Once a subject is registered in RPRS, the computer system will generate a randomly assigned arm. The UAMS Research Pharmacy will dispense study drugs after the subject has been randomized.

Investigational Product

Intrarosa® (Vaginal DHEA) Description

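### Randomisation may come up to 28 days before dispensing in an open-label trial, and nothing requires a usable baseline VMI before assignment

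*Combined protocol and SAP*

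**What the plan says.** In the Study Calendar (Appendix A), the row "Randomize to treatment arm" is marked only under Pre-Study/Baseline. Footnote a sets the window: "Pre-study/Baseline should be completed within 28 days prior to Day 1, Week 1". The row "Assigned treatment and study diaries dispensed to subject" is marked only under Day 1, Week 1. Footnote b adds that the "Day 1, Week 1 visit may be done the same day as Pre-Study/Baseline visit", provided baseline activities are done and eligibility is confirmed.

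The Randomization section gives the trigger: "Subjects who complete the screening will be randomly assigned to either" arm. It does not define screening. The arm is generated on registration in RPRS, and the pharmacy dispenses afterwards.

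Footnote i allows the gynaecologic exam, with pH and VMI, on the same day as consent and Day 1 if these are "completed after consent, all other eligibility criteria have been met, and prior to Day 1, Week 1 activities". It also lets a standard-of-care pelvic exam from the preceding 28 days be used. Footnote g lets questionnaires, including the QOL-CSV, be completed by phone. Footnote k and Study Design and Procedures require an unsatisfactory swab to be recollected within four weeks of Day 1. None of these provisions mentions randomisation.

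Under Efficacy and Safety Populations, subjects who stop "before 2 weeks of treatment will not be included in the efficacy population". The safety population requires at least one administration.

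**The concern.** Two things can happen between assignment and first dose in an open-label trial.

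First, women can leave because of the arm they drew. One arm is a moisturiser sold over the counter and the other is a prescription hormone precursor, so the reasons for leaving may differ by arm. Those who leave before dosing are in neither analysis population, so the compared groups are no longer the randomised ones.

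Second, a baseline value can be collected once the arm is known, or after treatment has begun. The primary endpoint is change in VMI from baseline, so an arm-related shift in baseline passes in full into the primary test. The follow-up ANCOVA reduces such a shift but does not remove it.

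**Working it through.** **1. Gap between assignment and dose.** The baseline block may start 28 days before Day 1 (footnote a) or fall on the same day (footnote b). The permitted gap is therefore 0 to 28 days. This is a ceiling; the documents do not give the typical gap.

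**2. What happens to a woman lost in that gap.** Efficacy needs two weeks or more on treatment and safety needs one administration. She has neither. With 30 per arm, one loss is 1/30 = 3.3% of an arm and three are 3/30 = 10%. The documents give no rate for such losses; zero to three is an assumed range.

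**3. Can a baseline follow assignment?**
- Repeat VMI swab: the calendar activity is to collect the swab and send it to pathology, so it is finished before the reading is known. Randomisation, and a same-day Day 1, can then precede an unsatisfactory report. The time limit on the repeat refers to Day 1 and does not say before or after. The repeat can fall after assignment and, with a same-day Day 1, after the first dose.
- pH: if a standard-of-care pelvic exam serves for eligibility, the study pH (and swab) may be taken at another contact, limited only to before Day 1 activities.
- QOL-CSV: completion by phone can separate it from the visit.

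The last two are lesser routes. They concern timing that is left open and do not describe an expected path.

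**4. Power.** Two-sample t-test, one-sided α = 0.05, effect 0.8 SD, noncentral t with df = n₁ + n₂ − 2 and noncentrality 0.8/√(1/n₁ + 1/n₂).
- Plan's figures: 30 v 30 (noncentrality 3.10, df 58) gives 92.2%; 24 v 24 (2.77, df 46) gives 86.1%. Both match the Sample Size and Power section. For the Wilcoxon test, multiplying n by 3/π gives 91.1% and 84.6%, against the stated 91.2% and 84.9%.
- Three pre-dose losses in one arm: 30 v 27 gives 90.9%. On top of 20% attrition, 24 v 21 gives 83.9%.

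Power falls by 1.3 and 2.2 points. Selection is the issue, not sample size.

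**5. Illustration of a shifted baseline (sizes assumed).** If arm knowledge moved one arm's mean change by b SD in favour of Intrarosa, the error rate with no true effect is the same calculation with b in place of 0.8, at 30 per arm:

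| b | Primary, nominal 5% | Secondary, nominal 1% |
|---|---|---|
| 0.1 | 10.3% | 2.6% |
| 0.2 | 19.0% | 5.8% |
| 0.3 | 31.0% | 11.7% |

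These are shifts in the arm mean. If k of 30 women have a late baseline and each is shifted by s SD, then b = k·s/30. Three women shifted by 1 SD each give b = 3 × 1/30 = 0.1. A few repeat swabs would therefore need large individual shifts to reach even the first row. The direction is not fixed either: a swab taken after effective dosing would raise the baseline in the Intrarosa arm and shrink its change, which works against the hypothesis.

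**The case against.** The strongest case is that the documents already imply the right order. Randomisation follows completed screening, and its row is the last one marked in the baseline column, below pH, swab, estradiol and QOL-CSV. Footnote i refers to all other eligibility criteria, which treats the gynaecologic exam as part of eligibility. Two exclusion criteria, vaginal disease and inability to tolerate a speculum, point to the same exam. Footnote i concerns same-day scheduling, and its silence on randomisation does not override the Randomization section. The repeat-swab limit may also be meant as the same four weeks before Day 1 as footnote a.

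Most of this stands. A reader might infer from the calendar that baselines are routinely taken with the arm known, or that every endpoint is exposed. The documents do not support either inference. Row order and screening language point to baseline first. The cytologists are blinded, which protects the VMI reading, though not the timing or sampling of the swab. The Secondary Efficacy Analyses also compare 12-week values unadjusted, and a shifted baseline cannot affect those tests.

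It is also fair that much of the harm from dropout comes from how the populations are defined. Women who stop within two weeks of starting are excluded wherever randomisation sits.

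What the objection does not remove is the separation of assignment from dispensing, and the absence of any link between a satisfactory VMI and randomisation.

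**Conclusion.** The point holds in a limited form. As written, assignment can precede dispensing by 0 to 28 days, and a woman lost in that interval is in neither analysis population. Baseline before randomisation is implied but not required, and the repeat-swab provision leaves a real opening for the primary endpoint's baseline. That opening rests on the swab result arriving after assignment; the documents give no laboratory turnaround time.

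The size of any bias is unknown. The documents supply no rate of pre-dose loss, no rate of unsatisfactory swabs and no evidence that either bias occurred. Each loss is 3.3% of an arm and the cost in power is small. This is a cheap improvement, of minor to moderate severity.

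**What to change.** Move the "Randomize to treatment arm" row to Day 1, Week 1, or as close to it as dispensing allows, as the last step before dispensing. In the Randomization section and in footnotes i and k, state that all baseline assessments are complete before RPRS randomisation: pH, estradiol, BSSC-W, FSFI, QOL-CSV, the supplemental survey, and a VMI reported as satisfactory. Make the same change where Study Design and Procedures describes the repeat swab.

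The cost is one calendar row and a few sentences. No sample-size input changes, and RPRS already assigns the arm on registration. There are two practical downsides: a same-day baseline and Day 1 would be limited by the cytology turnaround, and the pharmacy would learn the arm only on the dispensing day.

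This change does not address the exclusion of women who stop within two weeks of starting treatment. That is a separate matter for the efficacy population definition.
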